breathing patients with tracheostomy. However, since it still keeps airway open, the aerosol particle concentrations generated by patients via tracheostomy stoma as well as the virus load in the room air is still unknown. Thus this study is aimed to investigate the aerosol particle concentrations among different oxygen and humidification devices for spontaneous breathing patients with tracheostomy, in order to reflect the transmission risk.

Furthermore, our previous study found that wearing a surgical mask over high-flow nasal cannula can significantly reduce aerosol particle concentrations for COVID-19 patients,¹³ thus we also aim to explore the effects of wearing a surgical mask or using a scavenger tent over the high-flow device for tracheostomy patients can reduce the aerosol particle concentrations.

RUSH
Methods

IRB

Approved

1. Study design: a randomized cross-over trial
 - 1) Inclusion criteria: (1) adults; (2) tracheostomy; (3) able to spontaneous breathing without ventilator support.
 - 2) Exclusion criteria: (1) confirmed diagnosis of COVID-19 within recent two weeks; (2) non-English speaking; (3) refuse to participate in the study; (4) palliative care; (5) receiving ECMO; (6) unable to connect with tracheostomy adapter, such as laryngectomy tube.
 - 3) Reason for excluding COVID-19 patients in this trial is: the transmission risk of using different devices especially large volume nebulizer is still unknown, to protect the study investigators and other clinicians who might enter into the room with patients' airway open, we would not keep anyone inside the room with patient's airway open.

2. Comparisons: 1) high-flow high humidity device with tracheostomy adapter; 2) large-volume nebulizer (cool aerosol) with trach collar; 3) Venturi-adapter with trach collar; 4) large-volume nebulizer (cool aerosol) with T-piece and a filter; 5) high-flow high humidity device with tracheostomy adapter and a scavenger or a surgical mask over the adapter.
3. Sample size: This study is a superiority study. From our previous clinical study, wearing a surgical mask significantly reduced aerosol particle concentrations,¹³ particularly in proximity, the use of HMEF would reduce the aerosol particle concentrations even more, thus we expect the treatment effect would be medium to large as 0.1.¹⁴ Using G-power software¹⁵ to calculate the sample size in repeated ANOVA measures, with confidence level (α) of 95%, power ($1-\beta$) of 80%, the number of patients that need to be enrolled is 12.
4. Study process: after consent, respiratory therapist assesses patient to see if patient needs suctioning. If needed, suction patient. Place HMEF on patient for 10 mins in order to measure the baseline data. Then use different devices in a pre-determined random order (prepared in an opaque envelope) for 5 mins, followed by 10 mins HMEF for the baseline data (figure 1). Aerosol particle sizes (Model 3889, Kanomax, Andover, NJ) will be placed at 1 and 3 feet from the patient airway measure aerosol particle concentrations. Patient's comfort will be self-evaluated using an visual numerical scale (VNS) ranging between 1 (very uncomfortable) and 5 (very comfortable) (Figure 2).¹⁶
5. Data collection: age, gender, ethnicity, diagnosis, tracheostomy placement duration, tracheostomy tube size, cuff inflation, secretion amount and color, aerosol particle concentrations and patient comfort at baseline and during the use of different humidification devices

6. Outcome: 1) aerosol particle concentrations at baseline and during the use of different humidification devices; 2) patient comfort with different devices
7. Statistical analysis: Kolmogorov-Smirnov will be used to test normality of distribution for considered variables. Continuous variables will be expressed as mean (standard deviation [SD]) or median (Inter-Quartile Range [IQR]), depending on the normality of distribution. Friedman test will be used to compare the aerosol particle concentrations among five devices. A *p*-value of < 0.05 was considered statistically significant for all tests. Data analysis was conducted with SPSS statistical software (SPSS 26.0; SPSS; Chicago, IL).

References

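### The 80% power quoted for 12 patients belongs to a repeated-measures ANOVA; the planned five-device comparison is a Friedman test, for which no power is given

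*Combined protocol and SAP*

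**What the plan says.** Methods item 3 (Sample size) gives the effect as "we expect the treatment effect would be medium to large as 0.1", without naming the metric. It uses G*Power "to calculate the sample size in repeated ANOVA measures" and concludes, with power "of 80%, the number of patients that need to be enrolled is 12". The number of measures, the correlation between them and the nonsphericity value are not stated.

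Methods item 7 (Statistical analysis) names one test for the particle data: "Friedman test will be used to compare the aerosol particle concentrations among five devices". No condition is attached. The Kolmogorov-Smirnov check in the same item feeds only the descriptive reporting: "Continuous variables will be expressed as mean (standard deviation [SD]) or median (Inter-Quartile Range [IQR]), depending on the normality of distribution". ANOVA is not named there, and no power, sample size or efficiency adjustment for the Friedman test appears anywhere in the document.

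**The concern.** The 80% is the only stated justification for enrolling 12 patients, and a reader will take it as the power of the five-device comparison. It was computed for a different test. The Friedman test uses only within-patient ranks, so its power can be well below or well above that of the ANOVA, depending on the error distribution. The consequence is sharpest for a null result: it would be read against an 80% chance of detection that the plan does not support for the test actually run.

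**Working it through.** **Inputs from the plan.** Power 80%, N = 12, effect 0.1 and ANOVA sizing come from item 3; the Friedman test and five devices come from item 7. Item 3 writes "with confidence level (α) of 95" per cent, read here as α = 0.05, which agrees with item 7's "value of < 0.05 was considered statistically significant for all tests".

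**Inputs that must be assumed.** The metric of the 0.1, number of measures m, correlation ρ, sphericity and error distribution.

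**Step 1: reproduce the 12.** For a within-patient factor under sphericity, ANOVA power comes from a noncentral F with λ = N·m·f²/(1−ρ) and (m−1), (N−1)(m−1) degrees of freedom. Reading 0.1 as eta-squared gives f² = 0.1/0.9 = 0.111. With m = 5 and ρ = 0.5:

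- N = 11: λ = 11×5×0.111/0.5 = 12.2, df 4 and 40, power 0.756.
- N = 12: λ = 12×5×0.111/0.5 = 13.3, df 4 and 44, power 0.802.

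So 12 is the smallest adequate N under this reading. It is not the only reading that returns 12:

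- f² = 0.1, m = 6, ρ = 0.5: power 0.762 at N = 11 and 0.807 at N = 12.
- f² = 0.111, m = 4, ρ = 0.6: power 0.793 at N = 11 and 0.835 at N = 12.

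Reading 0.1 as Cohen's f does not fit: with m = 5 and ρ = 0.5 it needs 121 patients, and power at 12 is 0.11.

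**Step 2: power of the planned test.** With N = 12 and m = 5 the Friedman statistic is Q = 12/(N·m·(m+1))·ΣR² − 3N(m+1) = ΣR²/30 − 216, where R are the device rank sums. It is compared with the 5% chi-square point on 4 df, 9.488. Power was simulated with additive errors scaled to the same variance, 100,000 trials for each of six patterns of device means: linear, one higher, one lower, two extremes, two higher, two lower. The Monte Carlo standard error near 0.67 is √(0.67×0.33/100,000) ≈ 0.0015. The simulated type I error at N = 12 is 0.045 (200,000 trials).

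Normal errors, f² = 0.111, N = 12, five devices:

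| ρ | ANOVA | Friedman (range over patterns) |
|---|---|---|
| 0.3 | 64% | 0.502–0.522 |
| 0.4 | 72% | 0.575–0.596 |
| 0.5 | 80% | 0.664–0.688 |
| 0.6 | 89% | 0.773–0.793 |
| 0.7 | 96% | 0.887–0.905 |

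With f² = 0.1 and ρ = 0.5, Friedman power is 0.611–0.634 (ANOVA 0.753 with five devices).

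At f² = 0.111 and ρ = 0.5, Friedman power is 0.789–0.805 at N = 15 and 0.820–0.837 at N = 16. As a cross-check, the large-sample efficiency of Friedman relative to ANOVA under normality is 3m/(π(m+1)) = 15/(6π) = 0.796, and 12/0.796 ≈ 15.1.

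**Step 3: other error distributions.** Friedman, f² = 0.111, N = 12, five devices:

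| Errors | ρ = 0.5 | ρ = 0.3 |
|---|---|---|
| t, 5 df | 0.759–0.791 | not run |
| Laplace | 0.776–0.818 | not run |
| Lognormal, σ = 0.5 | 0.774–0.864 | 0.653–0.727 |
| Lognormal, σ = 1 | 0.929–0.994 | 0.883–0.979 |

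At ρ = 0.5 the low end of each lognormal range is the pattern with one device lower than the rest.

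**The case against.** The strongest reply is that the direction of the error is not established. Choosing a rank test suggests that non-normal data are expected. At ρ = 0.5 strong skew puts Friedman well above 80%, and above the ANOVA on the same data (0.836–0.842 for lognormal σ = 1). This stands, and it rules out calling the trial underpowered. It does not rescue the 80%, because the plan states no distribution. If the data are expected to be non-normal, the normal-theory sizing rests on a model the planners do not expect to hold.

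A second point concerns comparability. Two of the three input sets that return 12 do so with six or four measures, so their five-device Friedman figures mix a change of test with a change in the number of measures. Keeping each set's own number of measures gives Friedman power of 0.67–0.70 (six) and 0.69–0.71 (four), against ANOVA 0.807 and 0.835. The loss due to the test alone is therefore about 11 to 14 points in every set. The five-device figures answer a different question, the power of the comparison as planned. Under normal errors all three sets fall below 80% either way.

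Third, the pattern of device means matters and is not settled. The Introduction reports that "wearing a surgical mask over high-flow nasal cannula can significantly reduce aerosol particle concentrations for COVID-19 patients", which suggests one device lower. But two of the five listed set-ups add containment (a filter; a scavenger or mask), and with two devices lower the lognormal runs at ρ = 0.5 give 0.841 (σ = 0.5) and 0.983 (σ = 1). That is fair, and is why a range is needed.

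Finally, the unstated correlation moves Friedman power more (about 50% to 91% as ρ goes from 0.3 to 0.7) than the change of test does. That too is true, and is a reason to have the inputs written down.

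**Conclusion.** The concern holds. The stated 80% at 12 patients is the power of a repeated-measures ANOVA; the planned test is Friedman, and no power is given for it. This follows from items 3 and 7 alone and needs no assumption.

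The size does depend on assumptions. On the model that reproduces the 12 exactly (eta-squared 0.1, five measures, correlation 0.5, sphericity, normal errors), Friedman power is 66–69%, about 11 to 14 points short. Carrying all three input sets to the five devices under normal errors spans 61–79%. Non-normal errors or a higher correlation can bring it to 80% or beyond. So 80% is not established, and neither is a shortfall in every case. The mismatch does not bias estimates or inflate type I error. It should be corrected because it affects the only sample-size justification and is cheap to put right.

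**What to change.** Keep the Friedman test and the 12 patients. In Methods item 3:

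1. State what was entered in G*Power: effect-size metric, number of measures, correlation and nonsphericity value.
2. Label the 80% as the power of a repeated-measures ANOVA.
3. As the power of the planned test, give simulated Friedman power at N = 12 under those inputs, with a range over plausible correlations, error distributions and patterns of device means.
4. Say plainly that keeping 12 patients means accepting that this figure may be below 80%.

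An optional alternative is a log-scale repeated-measures or mixed model as primary analysis, so that sizing and analysis match, but only if the 0.1 effect can be justified on the log scale.

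The main fix costs a few sentences and one short simulation, with no change to the analysis or enrolment. The drawback is that the stated power becomes conditional on declared assumptions and, under a normal model, will probably be lower than 80%.

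### Section 7's only comparative test is an omnibus Friedman test, with no prespecified paired comparison or interval, so it cannot say which device differs or whether covering the high-flow device lowers particle concentrations

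*Combined protocol and SAP*

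**What the plan says.** The Introduction gives a lead aim: "this study is aimed to investigate the aerosol particle concentrations among different oxygen and humidification devices". Its last paragraph adds a second: "we also aim to explore the effects of wearing a surgical mask or using a scavenger tent", to see whether either one lowers concentrations around the high-flow device.

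Methods section 2 lists five conditions. Condition 1 is the uncovered high-flow device. Condition 5 is the "high-flow high humidity device with tracheostomy adapter and a scavenger or a surgical mask over the adapter". No other pair of conditions differs by the cover alone, so the second aim amounts to condition 5 against condition 1, although the document never writes it that way.

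Methods section 4 has every patient use the devices in random order. The particle counters "will be placed at 1 and 3 feet from the patient airway".

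Methods section 7 names four things:
- a Kolmogorov-Smirnov check of normality;
- summaries: "Continuous variables will be expressed as mean (standard deviation [SD]) or median" (with IQR);
- one comparative test: "Friedman test will be used to compare the aerosol particle concentrations among five devices";
- a threshold: p below 0.05 "was considered statistically significant for all tests".

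Neither section 7 nor any other section names a pairwise or post hoc test, an interval for a difference, or a multiplicity rule. Figure 1 is not shown, but its caption describes the study process, not an analysis.

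**The concern.** The Friedman test asks whether any of the five conditions differs from the others. A rejection does not identify the condition responsible. This limits the lead aim, because the plan never says how the devices would be separated after a significant result. It limits the second aim more, because that aim is a specific two-condition question.

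The document itself points to another likely source of a difference. The Introduction warns that large-volume nebulization can put bio-aerosol into the room, and Methods section 1 singles out that device's risk as unknown. A significant result driven by the unfiltered nebulizer (condition 2) would say nothing about the cover.

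The per-device means or medians would show a direction for 5 against 1. They would not give the size of the within-patient difference or its uncertainty, which is what a crossover design is well placed to supply.

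**Working it through.** **1. Reproduce the plan's sample size, to fix a scale.** Methods section 3 gives an effect ("we expect the treatment effect would be medium to large as 0.1"), repeated-measures ANOVA, 80% power and 12 patients. Alpha is read as 0.05. The metric of the 0.1 and the within-patient correlation ρ are not stated. Assume eta-squared = 0.1, five measurements, ρ = 0.5 and sphericity.
- f² = 0.1/0.9 = 0.111, so f = 0.333.
- λ = f² × 5 × N/(1 − ρ) = 0.111 × 5 × 12/0.5 = 13.3, with 4 and 44 degrees of freedom.
- Power is 0.802 at N = 12 and 0.756 at N = 11, so 12 is reproduced. (If 0.1 were Cohen's f, power at 12 would be 0.11.)

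The 12 patients are therefore sized for an omnibus five-condition comparison, not for 5 against 1.

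**2. Turn that effect into a shift of one condition.** The document gives no per-device effects, so assume that condition 2 alone carries the whole effect.
- With one of five means moved by d, the SD of the means is d × √(1/5 × 4/5) = 0.4d.
- In within-patient SD units, d = 0.333/0.4/√(1 − ρ). At ρ = 0.5 this is 0.833/0.707 = 1.18.

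**3. Simulate the planned test.** n = 12, five conditions, normal errors with within-patient SD 1, chi-square critical value 9.488, 200,000 runs.
- Conditions 1 and 5 identical, condition 2 shifted 1, 1.18, 1.5 or 2 SD: Friedman rejects 51%, 67%, 88% and 99%.
- In the same setting, a paired Wilcoxon test of 5 against 1 rejects about 4%, which is simply its size (exact 0.0425 at n = 12).
- Condition 2 shifted 1.18 SD and condition 5 also 1 SD lower: Friedman rejects 96%.

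The Friedman test therefore responds to a change in condition 5 but is not specific to it.

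**4. What a paired contrast would deliver with 12 patients** (one distance, same assumptions).
- The 95% CI half-width for 5 against 1 is about 2.201 × √(2/12) = 0.90 within-patient SD.
- As a single unadjusted contrast, power is 56% for a true difference of 1 SD and 89% for 1.5 SD.
- Under Holm over an illustrative three contrasts (5, 2 and 3, each against 1), after a significant Friedman test and with condition 2 at +1.18 SD, power is 40% and 79%.
- Under Holm over all ten pairs in the same setting, power is 23% and 60%.

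**5. How many covers each patient receives.** The Figure 1 caption gives 90 minutes in total. With 10 minutes of HMEF and 5 minutes of device per period:
- five periods take 5 × 15 = 75 minutes, or 85 with a closing HMEF;
- six periods take 6 × 15 = 90 minutes without one.

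Six periods would fit if each patient received both covers. The five devices named in section 7 point the other way, and 90 may be 85 rounded up. The document does not settle it.

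**The case against.** The second aim is worded as exploratory. In a 12-patient physiological crossover, reporting an exploratory question by per-device summaries is a limitation, and wanting a formal test is partly preference. That stands, and it keeps the point at a recommendation. It does not remove the gap, because even an exploratory answer needs an estimate of the paired difference with its uncertainty.

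The figures are also assumption-bound. The 67% depends on condition 2 carrying the whole effect, on ρ = 0.5 and on normal errors. With eta-squared held at 0.1, ρ from 0 to 0.8 moves the shift from 0.83 to 1.86 SD and the rejection rate from 36% to 98%, although N = 12 itself is reproduced only near ρ = 0.5. If concentrations were lognormal (log-scale within-patient SD 1, between-patient SD 0 to 2, assumed) and raw differences were tested, power for the single contrast at a 1 SD log-scale effect would fall from 56% to between 52% and 44%. These affect the size, not the logic.

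A reader might infer more than the document supports:
- *That the Friedman test is wrong or blind to the cover.* It suits a five-condition comparison and is sensitive to condition 5. What it lacks is specificity.
- *That the plan inflates false positives.* Unadjusted pairwise tests after a significant Friedman test would give at least one false difference among the other four devices in 14% to 19% of trials (condition 2 shifted 1 to 2 SD). But no such tests are in the plan, so this is a reason to specify them carefully, not an existing error.
- *That the gap belongs to the exploratory aim alone.* The lead comparison has the same omnibus limit.

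**Conclusion.** The point holds as a gap in the analysis plan. Followed as written, section 7 can say that some device differs but cannot attribute the difference to a particular device, and it leaves the covered-against-uncovered question to descriptive values. As a measure of size, with n = 12, no cover effect and condition 2 shifted by an assumed 1.18 within-patient SD, the planned test is significant about 67% of the time. The absence of a paired comparison or interval can be read directly from the text and needs no assumption. The 67% and the power figures rest on normal errors, the assumed correlation and the assumed pattern of device effects.

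It should be fixed, but it does not undermine the trial, because the aim most affected is exploratory. Nor does naming a distance alone make the contrast unique. The document also leaves open the scale, how readings over the 5 minutes are summarised, and whether each patient receives one cover or both.

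**What to change.** In section 7, after the Friedman test:
- Prespecify a short list of paired contrasts that includes condition 5 against condition 1. Test each by Wilcoxon signed-rank, with Holm adjustment if more than one is listed.
- Report each with its paired difference, or ratio if analysed on the log scale, and a 95% CI.
- Before data are seen, choose the scale, the primary distance (1 or 3 feet) and the summary of the 5-minute readings.
- State whether each patient receives one cover or both. If one, analyse mask and scavenger pooled as condition 5. If both, list mask against uncovered and scavenger against uncovered as two contrasts within the Holm family.
- Keep the cover aim labelled as exploratory.

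The cost is a few sentences and some power, with no extra patients. Under the assumptions above and a true difference of 1 SD, power for 5 against 1 is about 56% if it is the only contrast, 40% under Holm over three and 23% under Holm over all ten pairs, so the list should be short. If both covers are given to every patient there are two cover contrasts, and these power figures would need to be recalculated.
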